### **ABSTRACT**

Patients with chronic pain (PWCP) typically have multiple chronic conditions, and many points of contact with the health system. They can feel disempowered, and experience fragmented care and poor outcomes. PWCP report concerns about under-treatment of pain, difficulties in obtaining medication, and stigma. Prescription opioids are a very common, and controversial, pain treatment. PWCP often lack the skills and knowledge to talk to their physicians about their pain and opioid use, and to navigate the health care system. The study compared the effectiveness of an innovative behavioral Patient Activation plus Usual Care (PA+UC) intervention to Usual Care (UC) only on patient-centered outcomes among PWCP. With our stakeholder group of patient, clinical, and operational advisors, we conducted a pragmatic, randomized trial to examine the effectiveness of a group-based PA intervention in two large primary care clinics in an integrated health system. We randomized 376 PWCP to either the PA+UC arm or UC only arm. The curriculum covers patient activation and empowerment, how to talk to doctors about prescription opioid use, and self-management of chronic pain, including how to navigate the health care system and online patient portal. We developed the study questions, intervention curriculum, outcome measures, and dissemination plan with our stakeholder groups. We examined effects over 12 months using follow-up patient interviews combined with electronic health records (EHR) and a mixed effects modeling approach. Patient outcomes included patient-reported activation, quality of life, prescription opioid use, pain severity and function, patient-provider communication, patient satisfaction, self-care, including use of health information technology, and service utilization.

### **RESEARCH QUESTION**

Will a primary care-based behavioral intervention for patient activation and engagement and self-management, for patients with chronic pain who are taking opioid pain medication, result in better patient outcomes than Usual Care?

### **AIMS**

**Aim 1:** Refine and finalize a patient-driven intervention curriculum and patient-centered outcomes, developed with a stakeholder group.

**Aim 2:** Compare the effectiveness of Patient Activation + Usual Care (PA+UC) versus Usual Care (UC) on patient-centered outcomes.

Will patients in the PA+UC arm:

- a. Have greater improvement in patient activation, patient satisfaction, pain and function scores, quality of life and provider communication over time?
- b. Be more likely to engage in self-management strategies?
- c. Be more likely to actively use primary care, and decrease use of acute care services?

**Aim 3:** To compare the effectiveness of PA+UC versus UC on prescription opioid use. Will patients in the PA+UC arm be more likely to reach their goal for prescription opioid use and/or decrease their use over time?

### **SIGNIFICANCE**

Chronic non-cancer pain is widespread and debilitating, often involving multiple chronic health conditions, and is a burden on patients, their families, and health systems. The Institute of Medicine's 2011 report, "Relieving Pain in America" estimated that roughly 100 million adult Americans suffer from chronic pain, a number which only stands to increase due to an aging population and increasing chronic disease. It is one of the most common complaints presenting in primary care, and costs the U.S. between \$560-635 billion annually in health care and lost productivity. We focused on chronic non-cancer pain, since clinical considerations differ for individuals with a terminal condition.

Patients with chronic pain (PWCP) can have considerable work and social disability, compromised quality of life, loss of function, and isolation from family and friends. PWCP suffer from social stigma as well, and frequently from depression. The impact on patients' family members and community is also considerable, as we learned in our prior surveys and recent qualitative work with PWCP.

Prescription opioids are the most common medication used to treat pain, and their use has increased dramatically in recent years. However, long-term use, or chronic opioid therapy (COT), remains controversial; and evidence supporting COT for long-term pain and functional outcomes is mixed. There is considerable evidence and concern over associated harms. Increases in adverse events such as opioid abuse, falls, overdose and deaths associated with COT has led to what has been called a prescription opioid epidemic. The overdose rate in 2008 was nearly four times the rate in 1999, with 14,800 prescription opioid overdose deaths. Hospitalizations for prescription opioid poisoning doubled from 1999 to 2006. From 2004 to 2009, emergency room visits involving prescription opioids nearly doubled. From 1999 to 2009, drug abuse treatment admissions rates for non-heroin opiates grew over 400%. In 2010, 11.1% of persons age 18-25 used prescription opioids non-medically, and 1.4% were prescription opioid dependent. Patients may be unaware of long-term risks.

Federal agencies and health systems are responding to the increased rates of mortality and overdose with new initiatives related to opioid prescribing. The Food and Drug Administration (FDA) has issued Risk Evaluation and Mitigation Strategies (REMS) for training and education materials for prescribers of

long-acting opioids, and for manufacturers to obtain new drug approvals. Hydrocodone (e.g. Vicodin) has recently been reclassified as a Schedule II medication, and the FDA recently ordered new patient information labels on prescription bottles. Health systems have also initiated programs to reduce opioid prescribing, and dosages. For example, Group Health Cooperative (now Kaiser Permanente Washington) implemented an initiative to standardize prescribing practices and lower dosages to reduce risks associated with opioid use. It was a multi-faceted, primary care approach, designed with input from a variety of departments including “leaders in primary care, physical and rehabilitation medicine, clinical improvement, pharmacy, legal affairs, and other relevant departments to define new care processes that could be implemented”. Although ultimately intended to improve patient safety, it is not clear how patient-centered these types of initiatives are.

There is a unique tension in the experience of patients and providers with prescription opioids. Providers are reluctant to prescribe them because they are concerned both about scrutiny of their prescribing practices, about patients abusing them and other adverse events, and also feel frustration with this population. PWCP are often viewed as among the most difficult patients, because clinicians often feel they do not know how to help them. Patients, on the other hand, often have poor pain control, are afraid of losing access to their medication, and can find it difficult to talk with their provider. They do not want to be seen as the “difficult patient.” They often experience stigma from using prescription opioids, and feel they are treated with mistrust. They also may not feel “heard” by their physicians, and feel they are just being prescribed a pill. It is often easy to lose sight of the fact that patients and providers have the same goal: to reduce pain, and improve the functioning and quality of life of the patient.

Whom to talk with and how to get care is confusing for patients, particularly those with chronic illness. If they have more than one provider, they may not know which one is appropriate. In a pilot study of complex patients with multiple conditions, we found that those with pain frequently seek care at the emergency room. Health information technology (IT) can make it easier to communicate with and navigate the health system, but we have found pain patients often have not taken advantage of these resources, (e.g., not registering to email their physician). As part of Centers for Medicare and Medicaid Services (CMS) Stage 2 “meaningful use criteria”, web-based patient portals will be available to most health plans and federally qualified health centers (FQHC), but patients may need help to engage in use of these tools.

## **METHODS**

This was a randomized clinical trial in Adult Medicine, which compared a behavioral patient activation and pain self-management intervention to usual care for chronic pain patients using opioid pain medication.

**Study Site and Patients.** The study was located at the Santa Clara and San Jose Medical Centers of Kaiser Permanente Northern California, and led by a research team from the Kaiser Permanente Northern California Division of Research. The team included strong clinical research partnerships with the Chiefs

of Medicine at each site, [name] at Santa Clara and [name] at San Jose. The study sites were large primary care medical centers reflecting the diversity of the service area.

**Study Design.** The design was a pragmatic, randomized controlled trial with the patient as the unit of randomization. Eligible patients were those who used prescription opioids for a minimum of 3 days a week for the past 3+ months. We compared patient reported outcomes (see below) as well as health services use and prescription opioid use for those in the intervention arm to those who received usual care only (comparator group). We choose “usual care only” as the comparator group to best inform the intervention’s potential to enhance current practice. Usual care was determined by patients’ individual providers, according to practice guidelines related to specific conditions.

**Data Sources.** Patient-centered outcomes are reported from patient survey data at baseline, 6 and 12 months post recruitment. Pain is an individual experience, affected by individual factors, and patients and providers often have different definitions of treatment success. We assessed multiple domains to capture the patient experience. The EHR was the data source for patient clinical characteristics, patient portal use, prescription opioid use, and health services utilization.

### **Primary Outcome Measures**

*Patient Activation.* Measured by Patient Activation Measure (PAM), a 13-item instrument for measuring patient beliefs, knowledge and confidence for engaging in a wide range of health behaviors.

*Self-Efficacy.* The Pain Self-Efficacy Questionnaire (PSEQ) is an established 10-item measure of pain self-efficacy that is widely used in clinical settings to assess confidence in one's ability to work and lead a normal life despite pain.

*Quality of Life.* Measured by two dimensions of the PROMIS Global Health Scale- Physical Health and Mental Health.

*Depression.* Measured by the Patient Health Questionnaire-9 (PHQ-9), one of the most commonly used validated screening tools used to measure depression severity.

*Pain Coping.* Pain coping strategies and measures of functioning were assessed with the Chronic Pain Coping Inventory -42.

*Pain Severity and Functional Status.* Measured with the Patient-Reported Outcome Measurement Information System 29-item Health Profile (PROMIS-29) instrument. PROMIS is a system of highly reliable, precise and easy to implement measures of patient-reported outcomes in physical and mental health and social well-being, which can be used as primary or secondary endpoints in clinical studies of treatment effectiveness. The single pain-intensity item is used in raw form. We also assessed the respondent’s satisfaction with his/her overall sex life using the PROMIS Global Satisfaction with Sex Life. In addition, the survey asks questions about source and quality of pain (not part of the PROMIS-29).

*Patient Satisfaction.* Measured by patients' overall satisfaction with their overall health care, and their primary care doctor on a scale of "0" to "10," where "0" is the worst possible care and "10" is the best possible care.

*Patient Provider Communication.* Measured by the Communication Assessment Tool (CAT), a 14-item instrument, the CAT asks respondents to rate different dimensions of the communication and interpersonal skills of their physician using a 5-point rating scale. The Perceived Efficacy in Patient-Physician Interactions Questionnaire (PEPPI) was used to measure patients' self-efficacy in obtaining medical information and attention to their medical concerns from physicians.

*Prescription Opioid Use.* Pharmacy data on opioid dispensations were extracted and summarized from the EHR. We asked about patients' long-term goals for prescription opioid use among 4 categories: stay the same, increase, decrease, and stopping. Progress toward goals was assessed at 6 and 12 month follow-ups.

*Pain Management.* The survey asks questions about non-pharmaceutical pain management strategies.

*Opioid Misuse.* The Screener and Opioid Assessment for Patients in Pain (SOAPP) and Current Opioid Misuse Measure (COMM) were used to identify aberrant behaviors related to long-term opioid treatment.

*Other (non-opioid) Substance Use.* Drug, alcohol and tobacco use were collected from patient survey data.

*Health Care Utilization and Engagement.* Primary care services (number of non-urgent outpatient visits) and acute care services (number of emergency room visits and inpatient stays) within KPNC were extracted from the EHR. Questions on services received outside KPNC were included in the patient survey. Use of Kaiser's patient portal and health education programs were extracted from EHR and assessed by self-report.

**Patient Activation Group Intervention Sessions Curriculum.** The intervention consists of 4 group sessions, one meeting per week, led by a licensed psychologist trained in pain management.

Session 1: "Taking a Leading Role". This session focused on empowering patients to take a leading role in their pain management and overall healthcare. It provides patients with information about how pain manifests in the brain and the body via the Gate Control Theory of Pain, the long-term risks and side effects of prescription opioid use and how neuroplasticity can cause pain to become chronic in nature and render pain medications less effective, ineffective, or possibly even harmful over time. Patients were introduced to why mind, body, and behavioral methods of pain control are part of a comprehensive pain management package.

Session 2: "Lifestyle and Balance". This session discussed importance of healthy behaviors (e.g. exercise, sleep, caffeine, nutrition, alcohol, tobacco, and emotional health), and how they are related to chronic pain. This session provided interactive education on the stress response of the autonomic nervous system and how pain activates the stress response, thereby providing rationale for why learning how to

reduce sympathetic nervous system activity is crucial for a comprehensive pain management package. Patients had an opportunity to learn and practice several new pain management skills.

Session 3: “Navigating the health care system”. This session’s goal was to meet patients’ individual needs via active use of the KP online portal via smart phones or computers. The session included hands-on practice navigating kp.org, exploring Kaiser’s healthy lifestyle resources, as well as resources outside of KP.

Session 4: “Partnership and Prevention”. The last session focused on increasing patients’ confidence in discussing pain and self-management strategies with their primary care team, with a focus on assertive communication strategies.

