### **SAMPLE SIZE**

To power our main patient outcomes, we planned to recruit 324 patients. With a conservative sample retention rate of 80%, we estimated a final sample size of approximately 260 patients at the 12 month follow-up, which would provide power of .80 or higher for the proposed analyses. We surpassed our enrollment goal and our final sample size was 376. With a 90% retention rate, our final sample size of patients at the 12 month follow up was 342, allowing sufficient sample to power to test all research hypotheses.

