We illustrate power calculations for hypothesis testing based on our original proposed estimates, using worst case scenarios for each type of model used in the research aims, and assuming a Type 1 error rate of  $\alpha=.05$ . As an example of a continuous outcome, we consider the difference in activation scores between the Patient Activation (PA) + Usual Care (UC) and UC only groups. The cross-sectional analyses modeled by multivariate regression analyses will have a power of .80 to detect a conventionally small effect size of 0.07 with 12 independent covariates including the treatment group indicator, with a sample size of 260. We then examine the longitudinal analyses modeled by linear mixed-effects models. Assuming the worst case scenario of a correlation between the three repeated measures (baseline, 6 and 12 month questionnaires) to be 0.3 (analyses of prior studies indicate correlations of  $< 0.3$ ), the power to detect a 24% difference in standard deviation units will be .80 with a sample size of 230. As an example of power calculation for a binary response, we present statistical power for the likelihood of portal use between the PA+UC and UC groups. We will first examine the cross-sectional analyses modeled by multivariate logistic regression models. Based on results from an internally funded pilot study of complex patients, we expect an overall rate of portal use of 61%. The test of significance for an odds ratio of 2.5 for the coefficient of the indicator variable for treatment group (=1 if PA+UC, 0=UC), will have a power of .80 with a sample size of 166. In longitudinal analyses modeled by mixed-effects logistic models, using 3 repeated measures, for a worst case correlation of 30% between successive measurements, we will be able to detect a 12% difference between the PA+UC and UC groups with a power of .80 and sample size of 126 patients in each arm ( $n=252$ ). Given that our final sample size exceeded our original estimate, we have adequate power to examine main study questions.

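### All 13 outcome domains are labelled primary with no lead outcome, and the claim of power for every research hypothesis holds only one test at a time at alpha .05

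*Protocol*

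**What the plan says.** One heading, "Primary Outcome Measures", covers every outcome in the Protocol, from patient activation to health care utilization and engagement. No secondary or exploratory heading follows, and no domain, score or time point is singled out. Some entries read more like a data inventory than an endpoint, for example "Drug, alcohol and tobacco use were collected from patient survey data".

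The Aims section is narrower. Aim 2a asks whether the intervention arm will "Have greater improvement in patient activation, patient satisfaction, pain and function scores, quality of life and provider communication over time". Aim 2b asks about self-management, Aim 2c about primary and acute care use, and Aim 3 about prescription opioid use. The Abstract has a similar short list.

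The Sample Size section opens with "To power our main patient outcomes, we planned to recruit 324 patients". It illustrates power "using worst case scenarios for each type of model used in the research aims, and assuming a Type 1 error rate of" .05. Activation enters only as an illustration: "As an example of a continuous outcome, we consider the difference in activation scores". Portal use is introduced the same way. The section describes the 342 patients retained at 12 months as "allowing sufficient sample to power to test all research hypotheses", and it ends: "Given that our final sample size exceeded our original estimate, we have adequate power to examine main study questions". Neither the main outcomes nor the main questions are identified.

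**The concern.** When every domain is primary, a positive result on any one of them can be reported as a primary finding, and a reader cannot tell which result the trial was designed to deliver. If each domain is tested at .05, the chance of at least one false primary finding is well above 5%. The label also reaches beyond the trial's own questions: pain self-efficacy, depression and other substance use match no aim, nor does opioid misuse unless it is counted under Aim 3. All four are also absent from the Abstract's outcome list.

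The blanket power statement adds to the problem. It rests on single-test illustrations but is worded as if it covered the whole set, so it may be read as support for a family of primary outcomes that was never powered as a family.

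**Working it through.** **Count of domains.** Under the heading: activation, self-efficacy, quality of life, depression, pain coping, pain severity and function, satisfaction, communication, opioid use, pain management, opioid misuse, other substance use, utilization and engagement. Total 13.

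Matched to an aim: activation, satisfaction, pain and function, quality of life, communication (2a); pain coping and pain management (2b); utilization (2c); opioid use (3). Total 9. The count is 10 if opioid misuse is placed under Aim 3, and 8 if pain coping is not counted as self-management.

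**The Protocol's own figures.** Inputs from Sample Size: three measures, correlation 0.3, 0.24 SD, power .80, N=230. With compound symmetry, the variance of the mean of three measures is (1 + 2×0.3)/3 = 0.533.

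N = 4 × 0.533 × ((z_alpha + 0.842)/0.24)²

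- One-sided, z = 1.645: N = 229, which reproduces the stated 230.
- Two-sided, z = 1.960: N = 291.

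The longitudinal binary figure (12-point difference, 126 per arm) comes out at 128 per arm two-sided for 61% v 73%. So these are single-test figures at .05. Sidedness is not stated, and both versions are shown below.

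**Chance of at least one false primary finding**, one test per domain at .05:

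- 13 independent tests: 1 − .95^13 = .487
- 9 independent tests: 1 − .95^9 = .370

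Equicorrelated normal simulation, two-sided, 400,000 draws, correlations assumed:

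| Domains | r = 0 | r = .3 | r = .5 | r = .7 |
|---|---|---|---|---|
| 13 | 49% | 42% | 33% | 24% |
| 9 | 37% | 33% | 27% | 20% |

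One test per domain is a minimum, because several domains hold more than one measure (two communication scales, two misuse scales, two global health dimensions, several utilization counts).

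**Power at N=342 if 5% is held across the domains.** Allocation is assumed 1:1, so 171 per arm. For 0.24 SD: SE = sqrt(2 × 0.533/171) = 0.0790, and 0.24/0.0790 = 3.04. Power = Φ(3.04 − z).

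| Bonferroni, 0.24 SD | .05 | .05/9 | .05/13 |
|---|---|---|---|
| Two-sided | .86 | .60 | .56 |
| One-sided | .92 | .69 | .65 |

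For the 12-point difference, SE = sqrt((p1q1 + p2q2) × 0.533/171). Example, 55% v 67% at two-sided .05/13: SE = sqrt(0.4686 × 0.533/171) = 0.0382; 0.12/0.0382 = 3.14; Φ(3.14 − 2.89) = .60. Across 49 v 61, 55 v 67 and 61 v 73%:

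| Bonferroni, 12 points | .05/9 | .05/13 |
|---|---|---|
| Two-sided | .62–.69 | .57–.64 |
| One-sided | .70–.76 | .66–.72 |

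If portal data from the health record are available for all 376, the 13-domain ranges become .63–.70 and .71–.77. With nine domains, only the one-sided 61 v 73% case passes .80, at .81.

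**Other procedures that hold 5%.** Holm, average power for 0.24 SD (simulation, r from 0 to .5):

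- Two-sided: .56 (13 domains, one real effect) up to .74 (nine domains, all real).
- One-sided, every effect real: .77–.81 for 13 and .81–.85 for nine.

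A fixed testing order keeps the unadjusted power for whichever outcome comes first (.86 two-sided for 0.24 SD), but only for that one.

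**Cross-sectional illustrations** at .05/13 and N=342: the odds ratio of 2.5 keeps .87–.93. The effect size of 0.07, read as Cohen's f², keeps about .97–.98 as a 1-df treatment test, or .69 as the joint 12-df test that reproduces N=260.

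**The case against.** The strongest defence has four parts.

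- **The power statement can be read test by test.** The section says it illustrates power for each type of model at .05, and never claims joint power. On that reading it is not false: the longitudinal illustrations exceed .80 at N=342 even two-sided (.86 for 0.24 SD). This stands. The fault is that the sentence is unqualified while 13 domains carry the primary label.
- **Sharing of alpha belongs in a SAP, which is not shown.** This also stands, and the absence of a procedure is not counted here. A reader might infer that holding 5% must push both longitudinal illustrations below .80. The documents do not support that. It is true of Bonferroni at N=342, but one-sided Holm with every effect real can exceed .80, and a fixed order leaves the first outcome untouched. The aims are directional, and only a one-sided test reproduces N=230, so the one-sided reading cannot be dismissed.
- **The Abstract and Aims already indicate the main outcomes.** They do give a shorter list, and it is the natural reference for the undefined phrases in Sample Size. But neither names a lead outcome, and the primary heading overrides both.
- **Thirteen confirmatory tests is a construction.** No sentence says that every domain gets one, and 49% requires independence. Hence the ranges and the nine-domain figures. Even the lowest of these, 20%, is four times 5%.

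**Conclusion.** The concern holds for what the Protocol itself fixes: a primary label on all 13 domains with no lead outcome, main outcomes and main questions that are never defined, and a blanket power statement backed only by single-test illustrations. If each domain is tested at .05, the chance of at least one false primary finding runs from 24% to 49% for 13 domains and from 20% to 37% for the nine in the aims. These ranges assume one two-sided test per domain and between-outcome correlations from .7 down to 0.

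It would go too far to conclude that the trial is underpowered. With one named primary, power for 0.24 SD at N=342 is .86 two-sided, so naming it costs no patients. The loss from keeping several primaries depends on the procedure, the sidedness and how many effects are real. Measuring 13 domains is also not a fault in a patient-centred trial; calling all of them primary is.

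**What to change.** Choose one option.

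**A. One primary.** Name one outcome and one analysis, for example patient activation over 12 months by the mixed-effects model, and relabel the rest secondary or exploratory. Replace the claim about all hypotheses in Sample Size with: *The retained sample of 342 gives at least .80 power at alpha .05 for the primary outcome at the effect size below; other outcomes are not separately powered.*

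**B. A short named set.** Take the primaries from the aims, fix one measure for each, and state a procedure that holds 5% (Holm or a fixed order). Give power under that procedure, with its sidedness, separately for each type of outcome: continuous, binary, count or categorical. A single 0.24 SD figure cannot stand for portal use, visit counts or opioid goals.

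Under either option, make the phrases about main outcomes and main questions in Sample Size refer to the named set. Follow-up is complete and relabelling cannot by itself restore prespecification, so cite a dated record that the choice of outcome, or of measure per domain, preceded the results; failing that, disclose it as post hoc.

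The cost is text edits, a search for that record and, under B, adjusted p-values or an ordered test. Fewer outcomes can then be called confirmatory, and under B the stated power is less favourable.
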